9.2.2 Secondary Efficacy Analyses

9.2.2.1 Coefficient of Nitrogen Absorption

CNA at the end of each treatment period (Visit 6, Visit 9) will be analyzed. CNA will be expressed as the percentage of nitrogen (protein) absorbed from the subject's diet.

CNA will be calculated using 2 data points:

- Nitrogen consumption in grams as provided by the qualified dietitian at each site
- Nitrogen excretion in grams/24h as provided by the central laboratory

CNA will be calculated as follows:

$$\frac{(\text{Grams/24h of nitrogen consumed} - \text{Grams/24h of nitrogen excreted}) \times 100}{\text{Grams/24h of nitrogen consumed}}$$

The method for the analysis of CNA will be analogous to the method used for the primary efficacy analysis, as described in Section 9.2.1. For the analysis of CNA, if a subject switches study treatments (i.e. MS1819 to PERT or PERT to MS1819) during the confinement period, prior to the end of the stool collection, then the CNA value during that confinement period will be excluded from the analysis. Missing CNA values will not be imputed.

The 15% non-inferiority margin used for the primary efficacy analysis of CFA will also be applied to test the non-inferiority of MS1819-SD to porcine PERT in CNA at the end of each treatment period.

A secondary (supportive) analysis to the method for the analysis of CNA will be conducted using the per-protocol population, according to randomized treatment group.

In addition, CNA at the end of each treatment period (Visit 6, Visit 9) will be summarized by treatment group using descriptive statistics.

Nitrogen consumed (g/24h), nitrogen excreted (g/24h), and CNA (%) will be listed by visit for all subjects in the mITT population.

9.2.2.2 Stool Weight

Stool weight during the 72-hour marker-to-marker stool collections will be evaluated at the end of each treatment period (Visit 6, Visit 9). All collected stool will be shipped to the central lab for determination of the stool weight as described under the primary efficacy measure.

Stool weight at the end of each treatment period will be analyzed from stool samples collected during the 2 confinement periods (Visit 6 and Visit 9).

Stool weight at the end of each treatment period (Visit 6, Visit 9) will be summarized by treatment group using descriptive statistics. If a subject switches study treatments (i.e. MS1819 to PERT or PERT to MS1819) during the confinement period, prior to the end of the stool collection, then the stool weight value during that confinement period will be excluded from the summary.

If a subject has more than one stool weight record for a given visit (Visit 6 or Visit 9), only the heaviest value will be included in the summary.

Stool weight will be listed by visit for all subjects in the mITT population.

9.2.2.3 *Malabsorption Signs and Symptoms*

Signs and symptoms of malabsorption will be evaluated at Visits 3, 4, 5, 6, 7, 8, 9, and 10.

The EPI malabsorption symptoms will be evaluated according to the following measures:

- Stool frequency (number of bowel movements per day);
- Stool consistency (graded as 0 = hard, 1 = formed/normal, 2 = soft, 3 = watery, or 4 = overt diarrhea);
- Bloating (graded as 0 = none, 1 = mild, 2 = moderate, or 3 = severe);
- Abdominal pain (graded as 0 = none, 1 = mild, 2 = moderate, or 3 = severe);
- Flatulence (graded as 0 = none, 1 = mild, 2 = moderate, or 3 = severe);
- Incidences of visible oil/grease in stool (Yes/No).
- Increased stool quantity (graded as 0 = none, 1 = mild, 2 = moderate, or 3 = severe); and
- Worsening of overall bowel habit (graded as 0 = none, 1 = mild, 2 = moderate, or 3 = severe).

Stool frequency will be summarized by treatment group for the mITT population using descriptive statistics. Stool frequency will be summarized at Visit 3 (At Randomization), At First Dose, 1 Week Post First Dose, 2 Weeks Post First Dose, and 3 Weeks Post First Dose, as described in Section 3.

The number and percentage of subjects within each category for stool consistency, bloating, abdominal pain, flatulence, incidence of visible oil/grease in stool, increased stool quantity, and worsening of overall bowel habit at each study visit and by treatment group will also be provided Visit 3 (At Randomization), At First Dose, 1 Week Post First Dose, 2 Weeks Post First Dose, and 3 Weeks Post First Dose, as described in Section 3. Shifts from Visit 3 will be presented for stool consistency, bloating, abdominal pain, flatulence, increased stool quantity, and worsening of overall bowel habit for the mITT population by treatment group.

Signs and symptoms of malabsorption will be listed for all subjects in the mITT population.

9.2.2.4 *Weight and BMI*

Weight and BMI will be evaluated at Visits 1, 3, 6 and 9.

Weight and BMI at Visit 3 (At Randomization), At First Dose, and at 3 Weeks Post First Dose, as described in Section 3, will be summarized for the mITT population using descriptive statistics by treatment group.

Weight and BMI will be listed for all subjects in the mITT population.

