**Efficacy Analysis:**

- **Primary Efficacy Endpoint**

- **Primary Model of Analysis:** The primary endpoint (ie, the CFA assessed at the end of each 3-week treatment period [Visit 6 or Visit 9]), will be analyzed in a mixed model including terms for sequence (MS1819-PERT vs PERT- MS1819); random patient nested in sequence; period (1 vs 2); and treatment (MS1819 vs porcine PERT). The treatment effect, along with the 95% confidence interval (difference in adjusted CFA means, MS1819 minus porcine PERT), will be estimated in this model. Noninferiority will be claimed if the lower bound of the 95% confidence interval is greater than -15%, where 15% is the noninferiority margin. If noninferiority can be claimed, then superiority will be tested.

**Subgroup Analyses:** Analyses of CFA considering the same approach used for the primary set will be performed in the following subgroups:

- by CFA level while receiving porcine PERT (<80% vs  $\geq 80\%$ ). Of note, it is expected that about 75% of enrolled patients will have CFAs while receiving porcine PERTs of 80% or greater. An analysis will be done in the subgroup of patients with CFA below 80% while receiving porcine PERT, as well as in the subgroup of patients with CFA of 80% or greater while receiving porcine PERT.
- By those receiving or not receiving gastric acid suppression

- **Key Secondary Efficacy Endpoints**

- Stool weights, and signs and symptoms of malabsorption will be analyzed with the same approach used for the primary endpoint, switching non-parametric and semi-parametric methods employed in the case that model assumptions are violated.

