### 7.2.2 Secondary Efficacy Endpoints

The secondary efficacy endpoints of the study include:

- A comparison of 72-hour stool weights, MS1819-SD vs porcine PERT
- Signs and symptoms of malabsorption
  - Stool frequency (number of bowel movements per day)
  - Stool consistency (graded as 0=hard, 1=formed/normal, 2=soft, 3=watery, or 4=overt diarrhea)
  - Bloating (graded as 0=none, 1=mild, 2=moderate, 3=severe)
  - Abdominal pain (graded as 0=none, 1=mild, 2=moderate, or 3=severe)
  - Flatulence (graded as 0=none, 1=mild, 2=moderate, or 3=severe)
  - Incidence of visible oil/grease in stool (Yes/No)
  - Increased stool quantity (graded as 0=none, 1=mild, 2=moderate, or 3=severe)
  - Worsening of overall bowel habit (graded as 0=none, 1=mild, 2=moderate, or 3=severe)
- CNA
- Body weight
- Body mass index
- Serum liposoluble vitamins A, D, E and K

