#### **10.7.2 Secondary Efficacy Endpoints**

Coefficient of nitrogen absorption will be calculated and analyzed in the same manner as CFA.

Stool weights, and signs and symptoms for malabsorption will first be analyzed with the same approach used for the primary endpoint. Models for analyzing the secondary endpoints will be further detailed in the SAP. If these analyses reveal gross departures from model assumptions, a nonparametric or a (Hodges-Lehmann) semiparametric approach will be proposed to analyze non-normally distributed endpoints.

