3. GENERAL ANALYSIS AND REPORTING CONVENTIONS

The following is a list of general analysis and reporting conventions to be applied for this study.

Categorical variables will be summarized using counts (n) and percentages (%) and will be presented in the form “n (xx.x).” If a count is 0, 0% will be shown for the percentage. To ensure completeness, summaries for categorical and discrete variables will include all categories, even if no subjects had a response in a particular category.

Continuous variables will be summarized using mean, SD, minimum, maximum, median and number of subjects. The 25th and 75th percentiles will be provided for distributions that are known to be skewed. The mean, median, 25th percentile, 75th percentile, and confidence intervals (CI) will be reported to 1 more level of precision than the original observations, and the SD will be reported to 2 more levels of precision than the original observations. The minimum and maximum will be the same precision as the original data.

When p-values are provided, they will be rounded to 3 decimal places; p-values that round to “0.000” will be presented as “<0.001.” Unless otherwise stated, all statistical tests of treatment effects will be conducted at a 2-sided alpha level of 0.05.

All analysis will be performed using SAS® System version 9.3 or later.

Dates in listings will be displayed as yyyy-mm-dd (e.g., 2015-01-24).

In general, age will be calculated in years using the date of birth and the date of randomization as [(date of randomization – date of birth)]/365.25, rounded down to the next largest integer using the floor function. For any listing that includes screen failures, age will be labeled as age at screening and will be calculated in years using the date of birth and the date of Visit 1 as [(date of Visit 1 – date of birth)]/365.25, rounded down to the next largest integer using the floor function.

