10. DATA MONITORING

10.1 Data Monitoring

An external, independent Data and Safety Monitoring Board (DSMB) consisting of members of the Cystic Fibrosis Foundation Therapeutics, Inc. (CFFT) DSMB, will monitor safety throughout the trial. After the study is complete, the DSMB will review the efficacy/safety data. Additional safety reviews may be conducted, at the request of the Data Safety Monitoring Board (DSMB) or DSMB Chair.

Since the planned DSMB review will occur after the completion of the study, the DSMB will review a subset of the analyses specified in the SAP and a separate DSMB analysis plan is not required.

Details are described in the DSMB charter.

11. DIFFERENCES BETWEEN THE SAP AND PROTOCOL AND CHANGES TO THE ANALYSES PLANNED IN THE PROTOCOL

No subjects were enrolled under the original protocol, so only differences between the SAP and protocol and changes to the analyses planned in Version 2.0 of the protocol are described below.

11.1 Differences between the SAP and Protocol and Changes to the Analyses Planned in Protocol Version 2

In section 10.7.2, the protocol states that stool weight and signs and symptoms of malabsorption will be analyzed with the same approach used for the primary endpoint. Instead, stool weight will be summarized using descriptive statistics. Since the signs and symptoms of malabsorption are categorical variables, this SAP specifies that these variables will be summarized by frequency tables in order to preserve the most information and given that it may not be reasonable to treat the differences between categories as uniformly quantifiable.

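### In the SAP text, stool weight and stool frequency get by-treatment summaries only, so the within-patient difference and 95% CI planned in the protocol are no longer prespecified

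*SAP*

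**What the plan says.** **Protocol.** Under the synopsis heading "Key Secondary Efficacy Endpoints" it states: "Stool weights, and signs and symptoms of malabsorption will be analyzed with the same approach used for the primary endpoint". Section 10.7.2 repeats that these endpoints "will first be analyzed with the same approach used for the primary endpoint", and offers a nonparametric or Hodges-Lehmann approach if model assumptions fail grossly. The primary approach (Section 10.7.1) is a mixed model with sequence, period, treatment and random patient within sequence, giving the MS1819 minus PERT difference with a 95% CI. Section 7.2.2 defines the stool-weight endpoint as "A comparison of 72-hour stool weights, MS1819-SD vs porcine PERT" and lists stool frequency, a number per day, among the signs and symptoms.

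**SAP.** Section 2.1.2 keeps the objective of comparing the two treatments on stool weight and on malabsorption signs and symptoms. Section 9.2.2.2 then says "Stool weight at the end of each treatment period (Visit 6, Visit 9) will be summarized by treatment group using descriptive statistics", and Section 9.2.2.3 says "Stool frequency will be summarized by treatment group for the mITT population using descriptive statistics". Section 3 defines such summaries: "Continuous variables will be summarized using mean, SD, minimum, maximum, median and number of subjects". It adds quartiles for skewed distributions and mentions confidence intervals only when setting decimal places.

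**Declaration of the change.** SAP 11.1 says of the protocol's plan: "Instead, stool weight will be summarized using descriptive statistics". For the signs and symptoms it substitutes frequency tables, because the variables are categorical.

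**The concern.** The SAP keeps the aim of comparing treatments but drops the analysis that would make the comparison for two numeric endpoints. SAP 11.1 gives no reason for stool weight. Its reason for the symptoms suits the graded and yes/no items, but stool frequency is a count, and SAP 9.2.2.3 itself summarizes it with continuous-variable statistics rather than a frequency table. If non-normality was the worry, Protocol 10.7.2 already had a fallback. Feasibility is not the obstacle: CNA, from the same collections, keeps the primary-type mixed model in SAP 9.2.2.1.

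At stake is a prespecified, within-patient estimate of uncertainty for two supportive measures. The listings would let someone compute one later, but only as a post hoc analysis of an open-label trial.

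**Working it through.** The documents give no SD, correlation or target precision for stool weight or stool frequency, so there is no planned figure to reproduce, and results are in SD units. Inputs: 30 patients completing both periods, 15 per sequence (SAP 2.2); 38 enrolled to allow for 20% dropout (SAP 2.6). The within-patient correlation r is assumed.

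**1. Point estimate, completers only.** Let A be MS1819-PERT and B be PERT-MS1819. The period-adjusted estimate is half the between-sequence difference in mean Period 1 minus Period 2 values:

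½[(MS_A − PERT_A) − (PERT_B − MS_B)] = ½(MS_A + MS_B) − ½(PERT_A + PERT_B)

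With 15 patients in each sequence, the right-hand side is the difference between the two printed column means. For balanced completers the point estimate is therefore not lost.

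**2. Crossover interval.** SE = ½ × SD_d × √(1/15 + 1/15) = SD_d/√30, where SD_d is the SD of the paired differences. With 28 df, t = 2.048, so the half-width is 2.048/√30 = 0.374 SD_d. Since SD_d = √(2(1 − r)) × the SD of a single measurement, the half-width can also be put on that scale (table below).

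**3. Interval from the two columns.** A reader with only two means and SDs can form only an unpaired interval. With 58 df, t = 2.002, so the half-width is 2.002 × √(2/30) = 0.517 single-measurement SD.

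| Assumed r | Crossover half-width (single-measurement SD) | Unpaired half-width | Ratio, unpaired to crossover |
|---|---|---|---|
| 0 | 0.529 | 0.517 | 0.98 |
| 0.3 | 0.443 | 0.517 | 1.17 |
| 0.5 | 0.374 | 0.517 | 1.38 |
| 0.7 | 0.290 | 0.517 | 1.78 |

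At r = 0 pairing gains nothing and costs a little in degrees of freedom. The gain grows with r.

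**4. One-period patients.** Suppose the 8 expected dropouts (38 − 30) split 4 and 4 and all leave after the Visit 6 collection. Each column then holds 34 values: the 30 completers plus 4 patients seen on that treatment only. The raw difference in means shifts by 4/34 × (gap_MS − gap_PERT) = 0.118 × (gap_MS − gap_PERT). Each gap is the mean of the 4 extra patients minus the mean of all 30 completers in the same column. The shift is zero if the two gaps are equal, and patients who leave before Visit 6 add nothing. The documents give no basis for a value of either gap.

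**The case against.** The other side has a good deal.

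- **Permitted and declared.** Protocol 10.7.2 leaves secondary models to the SAP, Protocol 10.1 allows changes that touch no principal feature, and SAP 11.1 states this one. A reader might infer an undisclosed or forbidden departure; the documents do not support that.
- **Safety-led Phase 2 trial.** Protocol 10.1 puts safety first, does not expect inferential results to reach significance, and applies no multiplicity adjustment to secondary endpoints. Descriptive reporting is defensible in that setting. It does not argue against an interval, though, which is the natural way to show limited precision.
- **Status of the endpoints.** A reader might take the synopsis heading to mean a testing hierarchy has been broken. The word key appears only there; Protocol 7.2.2 and 10.7.2 say secondary, and no order or alpha is attached.
- **Size.** The width ratios rest on an assumed correlation and on a reader who uses only the two columns, although the SAP lists individual values.
- **Table specifications.** SAP 1 and SAP 14 place these in separate documents that were not available. They might show a difference and CI, so the point is confined to the SAP text.

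These limits reduce the weight of the point. They do not supply the missing comparison, a reason for stool weight, or a reason that fits stool frequency.

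**Conclusion.** The point holds as a minor one. In the SAP text, neither stool weight nor stool frequency has a prespecified treatment difference with SE and 95% CI, although the protocol planned one and SAP 2.1.2 still calls for a comparison. With balanced completers the point estimate can be recovered from the printed means, so the main loss is the within-patient measure of uncertainty. Its half-width would be 0.374 SD of the paired differences with 30 completers, against an unpaired interval 0.98, 1.17, 1.38 or 1.78 times as wide at assumed correlations of 0, 0.3, 0.5 or 0.7. Nothing can be stated in grams or stools per day.

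Two stronger readings are not supported. One is that the summaries are biased: one-period patients could shift the raw difference, but no actual bias is shown. The other is that the efficacy conclusion is weakened: the CFA analysis is untouched. Frequency tables for the graded and yes/no symptoms are not in question, because the SAP's reason fits them. Nor are the descriptive summaries of weight, BMI and vitamins, for which Protocol 10.7.2 names no model.

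**What to change.** Keep the descriptive tables and add the following to SAP 9.2.2.2 and 9.2.2.3.

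- **Model.** For stool weight (Visits 6 and 9), and for stool frequency three weeks after first dose of each treatment (also Visits 6 and 9), fit a mixed model with sequence, period, treatment and random patient nested in sequence. Report the LS mean difference MS1819-SD minus porcine PERT, its SE and 95% CI, as secondary estimates with no noninferiority margin and no multiplicity control.
- **Sensitivity analysis.** Report alongside it the Hodges-Lehmann estimate and 95% CI: half the between-sequence shift (MS1819-PERT minus PERT-MS1819) in within-patient Period 1 minus Period 2 differences. Reporting both avoids choosing the estimator after seeing the residuals.
- **One-period patients.** State that they contribute to the mixed model only, under missing-at-random, and that the Hodges-Lehmann estimate uses only patients with both periods.
- **Covariate, if wanted.** If gastric acid suppression is included to match CFA and CNA, define it as use at randomization, as in SAP 6. Protocol 7.5 bars altering or stopping these drugs but does not expressly bar starting them.
- **SAP 11.1.** Correct it to match. Declare the stool-frequency time point as a SAP choice (Protocol 10.7.2 names none), the use of Hodges-Lehmann as a sensitivity analysis rather than a fallback, and the covariate if used. Confine the categorical reason to the graded and yes/no symptoms.

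Cost: SAP wording and two extra model outputs, each with its Hodges-Lehmann companion. No new data are needed.

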9.2.2.5 Serum Liposoluble Vitamin (A, D, E, and K) Levels

Analyses of certain lab values will be undertaken to evaluate markers of nutritional status. Specifically, the laboratory parameters to be summarized will include blood levels of vitamin A, D, E, and K. Vitamin A, D, E, and K levels will be evaluated at Visits 1, 3, 6, 9, and 10.

Vitamin A, D, E, and K levels will be summarized by treatment group for Visit 3 (At Randomization), At First Dose, and at 3 Weeks Post First Dose, as described in Section 3, using descriptive statistics.

Vitamin A, D, E, and K levels will be listed for all subjects in the mITT population.

10. DATA MONITORING

10.1 Data Monitoring

An external, independent Data and Safety Monitoring Board (DSMB) consisting of members of the Cystic Fibrosis Foundation Therapeutics, Inc. (CFFT) DSMB, will monitor safety throughout the trial. After the study is complete, the DSMB will review the efficacy/safety data. Additional safety reviews may be conducted, at the request of the Data Safety Monitoring Board (DSMB) or DSMB Chair.

Since the planned DSMB review will occur after the completion of the study, the DSMB will review a subset of the analyses specified in the SAP and a separate DSMB analysis plan is not required.

Details are described in the DSMB charter.

11. DIFFERENCES BETWEEN THE SAP AND PROTOCOL AND CHANGES TO THE ANALYSES PLANNED IN THE PROTOCOL

No subjects were enrolled under the original protocol, so only differences between the SAP and protocol and changes to the analyses planned in Version 2.0 of the protocol are described below.

11.1 Differences between the SAP and Protocol and Changes to the Analyses Planned in Protocol Version 2

In section 10.7.2, the protocol states that stool weight and signs and symptoms of malabsorption will be analyzed with the same approach used for the primary endpoint. Instead, stool weight will be summarized using descriptive statistics. Since the signs and symptoms of malabsorption are categorical variables, this SAP specifies that these variables will be summarized by frequency tables in order to preserve the most information and given that it may not be reasonable to treat the differences between categories as uniformly quantifiable.

13. APPENDICES

13.1 Study Flow Chart

A Phase 2, Open-Label, Multicenter, 2x2 Crossover Trial to assess the Safety and Efficacy of MS1819-SD in Patients with Exocrine Pancreatic Insufficiency due to Cystic Fibrosis

13.2 Schedule of Events

Schedule of Assessments

	SCREENING		INITIAL TREATMENT PERIOD				SECOND TREATMENT PERIOD			END OF STUDY/EARLY TERMINATION
	1 ^a	2 (T) ^b	3	4 (T) ^c	5 (T) ^c	6 ^d	7 (T) ^c	8 (T) ^c	9 ^d	
Visit Number	1 ^a	2 (T) ^b	3	4 (T) ^c	5 (T) ^c	6 ^d	7 (T) ^c	8 (T) ^c	9 ^d	10
Study Week	-3		1	1	2	3	4	5	6	8
Study Days	-21		1	8	15	17	29	36	38	56
Visit Window (days)	V1 to V2 interval ≤21 days			±2	±1	±7	±2	±2	±7	±2
Pre-Visit Instructions		X								
Supervised confinement						X			X	
Clinical Assessments										
Obtain informed consent	X									
Demographics	X									
Complete history and physical	X									
Focused physical exam ^e			X			X			X	X
Confirm CF diagnosis	X									
Height/weight, vital signs (sitting)	X		X			X			X	
Inclusion/exclusion criteria review	X		X							
Concomitant medications	X		X	X	X	X	X	X	X	X
Adverse events	X		X	X	X	X	X	X	X	X
Confirm scheduled date for next supervised confinement visit				X	X		X	X		
Study Treatment										
Randomization			X							
Instruct regarding prestudy										
PERT/Dispense study drug			X			X			X	
MS1819-SD										
Verify study drug						X			X	

	SCREENING		INITIAL TREATMENT PERIOD				SECOND TREATMENT PERIOD			END OF STUDY/EARLY TERMINATION
Visit Number	1 ^a	2 (T) ^b	3	4 (T) ^c	5 (T) ^c	6 ^d	7 (T) ^c	8 (T) ^c	9 ^d	10
Study Week	-3		1	1	2	3	4	5	6	8
Study Days	-21		1	8	15	17	29	36	38	56
Visit Window (days)	V1 to V2 interval ≤21 days			±2	±1	±7	±2	±2	±7	±2
count at the end of confinement										
Return MS1819-SD (only for those on MS1819-SD) at the end of confinement						X			X	
Record fat and protein intake and study drug taken at all meals and snacks						X			X	
Cross over to alternative treatment ^f						X				
Efficacy Measures										
Malabsorption signs & symptoms			X	X	X	X	X	X	X	X
72-hour controlled diet record						X			X	
Marker-to-marker stool collection and stool weight ^g						X			X	
Laboratory Tests										
Urinalysis	X		X			X			X	
Pregnancy test (serum for V1 screening and urine dipstick for other visits) ^h	X		X			X			X	X
Hematology, clinical chemistry, PT/INR, and aPTT ⁱ	X					X			X	
Fasting lipids (patient to come in fasting status) and pre-albumin	X					X			X	

	SCREENING		INITIAL TREATMENT PERIOD				SECOND TREATMENT PERIOD			END OF STUDY/EARLY TERMINATION
Visit Number	1^a	2 (T)^b	3	4 (T)^c	5 (T)^c	6^d	7 (T)^c	8 (T)^c	9^d	10
Study Week	-3		1	1	2	3	4	5	6	8
Study Days	-21		1	8	15	17	29	36	38	56
Visit Window (days)	V1 to V2 interval ≤21 days			±2	±1	±7	±2	±2	±7	±2
Vitamin A, D, E, and K	X		X			X			X	X
Serum samples for anti-LIP2 lipase antibodies and MS1819-SD concentrations			X			X			X	X
Fecal pancreatic elastase ^j	X									
Diagnostic Test										
Spirometry	X									
Resume Prescribed PERT										
Switch back to prescribed porcine PERT ^k									X	

^A Screening procedures can occur up to 21 days before V1 through the first day of dosing (V3).

^B This first study telephone call will occur once eligibility for the patient is determined. Instructions on the randomization visit will also be communicated and patients will be told to bring in their prestudy porcine with them for V3.

^C Visits 4, 5, 7, and 8 are telephone visits to assess any changes to AEs and concomitant medications in addition to confirming the visit date for the next scheduled supervised confinement.

^D Visit 6 and Visit 9 are the first and second scheduled confinement visits and can take up to 7 days. A 7 day window is permitted around the scheduled confinement for both V6 and V9 to accommodate for scheduling. Patient should bring their prestudy porcine PERT to V3.

^E The Focused Physical Exam will evaluate gastrointestinal tract, heart, and lungs.

^F At the end of V6 (after the last stool sample has been collected), Patients that were randomized to MS1819-SD will begin treatment with their prestudy porcine PERT. Patients that were randomized to their prestudy porcine PERT will begin treatment with MS1819-SD.

